4.4.3 Total Nasal Symptom Score (TNSS)

The TNSS is an instrument used to collect patient self-rated severity of nasal symptoms originally comprised of 3 symptoms (nasal obstruction, itching/sneezing and secretion/runny nose)¹⁵ that has been widely adapted to include 4 nasal symptoms: rhinorrhea, nasal congestion, nasal itching, and sneezing. The FDA has cited the TNSS as a preferred measure of efficacy in trials of drug treatments for allergic rhinitis¹⁶ and nonallergic rhinitis.¹⁷ The TNSS requires the patient to rate 4 nasal symptoms (rhinorrhea, nasal congestion, nasal itching and sneezing) on the following 4-point scale:

- 0 =absent symptoms (no sign/symptom is evident)
- 1 = mild symptoms (sign/symptom present, but minimal awareness; easily tolerated)
- 2 = moderate symptoms (definite awareness of sign/symptom that is bothersome but tolerable)
- 3 = severe symptoms (sign/symptom that is hard to tolerate; causes interference with activities of daily living and/or sleeping).

The total score is the sum of the 4 nasal symptom scores with a maximum TNSS of 12 indicating the most severe symptoms.

The minimal clinically important difference (MCID) for change in mean TNSS derived from anchor-based methodologies has been shown to be 0.23 - 0.28 units and by distribution-based methodology the MCID was determined to be 0.59 units.¹⁸ A less rigorous expert panel-based estimate of the MCID was 30% of the maximum score of 12, which is 3.6 units.¹⁹ The evidence-based

RhinAer RELIEF single arm protocol Rev C Final 27JAN2021CONFIDENTIAL

thresholds for MCID have been recommended to supersede the panel-based method. $^{\rm 20,21}$

The 24-hour reflective TNSS (rTNSS) will be used in this study. Participants will be asked to self-evaluate their symptom severity over the preceding 24 hours.

Treatment Responder based on rTNSS improvement

Individual participant success (responder) is defined as at least 30% improvement (decrease) in the rTNSS from baseline.

4.4.4 Mini Rhinoconjunctivitis Quality of Life Questionnaire (MiniRQLQ)

The Rhinoconjuctivitis Quality of Life Questionnaire is a well-established, validated, and the most frequently used rhinoconjuctivitis disease-specific instrument.²² The original RQLQ consisted of 28 questions across 7 domains and included ratings of 3 activities selected by the patient.²³ The validated standardized version (RQLQ(S)) uses standardized activity questions, which facilitates ease of administration.²⁴ The MiniRQLQ, to be used in this study, was developed and validated to further facilitate ease of use and efficiency by reducing the number of questions to 14.²⁵ The RQLQ(S) and the MiniRQLQ were found to be the best tests with optimal discriminant validity and responsiveness for measurement of health-related quality of life in AR patients.²⁶ While much of the development and validation of the RQLQ instruments have occurred in AR patients, the MiniRQLQ has also been validated for NAR patients.²⁷

The instrument consists of 14 questions across 5 domains (activity limitations (n=3), practical problems (n=2), nose symptoms (n=3), eye symptoms (n=3), and other symptoms (n=3)). Responses are based on a 1-week recall and provided on a 7-point scale:

- 0 = not troubled
- 1 = hardly troubled at all
- 2 = somewhat troubled
- 3 =moderately troubled
- 4 = quite a bit troubled
- 5 = very troubled
- 6 = extremely troubled.

The total or overall MiniRQLQ score is the mean of the 14 responses and the domain scores are the mean of the questions in each domain.

The generally accepted MCID for the overall RQLQ(S) and each individual domain is $0.5^{22,24,28,29}$ and has also been reported as ≥ 0.62 .³⁰ The developers of the RQLQ instruments reported that the MCID for the MiniRQLQ was slightly

RhinAer RELIEF single arm protocol Rev C Final 27JAN2021CONFIDENTIAL

higher (0.7) than for the RQLQ(S).²⁵ Another study using a combination of both anchor-based and distribution-based methods determined the MCID for the MiniRQLQ to be 0.42 (95% confidence interval 0.30 - 0.51).³¹

4.4.5 Participant Satisfaction

Satisfaction with the procedure is measured with a five-question self-reported survey using a 5-point scale to assess tolerability of the procedure, ease of recovery, change in drainage/rhinorrhea/runny nose symptoms, overall satisfaction with the procedure, and recommendation to others

4.4.6 Other Rhinitis Symptoms - Cough and Postnasal Drip

Self-reported assessment of current problems with cough and postnasal drip or excess mucous in the throat rated on the same 4-point scale used for symptoms comprising the rTNSS:

- 0 =absent symptoms (no sign/symptom is evident)
- 1 = mild symptoms (sign/symptom present, but minimal awareness; easily tolerated)
- 2 = moderate symptoms (definite awareness of sign/symptom that is bothersome but tolerable)
- 3 = severe symptoms (sign/symptom that is hard to tolerate; causes interference with activities of daily living and/or sleeping).

4.4.7 Change in Amount of PRN Medication/Device Use for Chronic Rhinitis Symptoms

Self-reported assessment of an increase or decrease from baseline in as needed medications and/or devices used for treatment of nasal symptoms following the procedure.

4.4.8 Medication and Other Therapies for Symptoms of Chronic Rhinitis

The current use of medication, devices, or other therapies for symptoms of chronic rhinitis, medication name, frequency, and dose will be recorded at each evaluation visit. Medications may be categorized for reporting purposes.

4.4.9 Adverse Events

Adverse events will be documented according to Section 7.1.

4.5 Success/Failure Criteria

Determinations of the successfulness of the treatment will be made on 2 levels: the individual participant level and in terms of the overall change in mean rTNSS from baseline to 3 months after the procedure.

4.51 Participant Success

The success measure for individual participant success (responder) is defined as at least 30% improvement (decrease) in the rTNSS from baseline at the 3month primary endpoint.

4.5.2 Participant Failure

A participant will be considered a nonresponder at the 3-month evaluation if the success criterion has not been attained.

4.5.3 Study Success

The study will be considered a success if the mean change from baseline of the rTNSS at 3 months significantly exceeds the MCID set for the study.

4.6 Duration of the Study

The primary outcome will be evaluated at 3 months. In addition, evaluations at 6, 12, 24, and 36 months after treatment will extend follow-up to 3 years for evaluation of longer-term efficacy. Enrollment is anticipated to be completed within 6 months. Therefore, total study duration is anticipated to be approximately 42 months.

4.7 Site Staffing and Responsibilities of Study Personnel

The principal investigator is responsible for ensuring that he/she has sufficient and qualified staff to conduct the clinical study and that all study-related tasks have been appropriately delegated and documented.

The treating physician will perform the procedure and discharge and 3-month followup assessments. The treating physician must be a medical doctor with experience in ENT procedures and trained in administering the RhinAer procedure.

Remote follow-up will be performed by medical or office staff with relevant knowledge and experience as determined by the principal investigator to interact with study participants to ensure collection of study data and participant reported outcomes.

4.8 Device Description

The RhinAer procedure incorporates use of the RhinAer Stylus (Model FG815), which is a cleared (FDA - K192471) disposable handheld device capable of delivering bipolar radiofrequency energy to tissue. RhinAer has CE Marking in EU. The Aerin Console (Model FG226) RF generator with temperature control capable of delivering very low doses of energy was cleared for use in the US (FDA - K162810) and has CE Marking in the EU (CE639608)

The RhinAer Stylus (Figure 1) consists of a handle, shaft and treatment tip. An array of bipolar electrodes is positioned on a nonconductive tip (Figure 2) that is attached to the handle via a nonconductive shaft. A temperature sensor is located on the Stylus tip to monitor tissue temperature during RF energy delivery. The Stylus is powered by an external temperature-controlled radiofrequency generator via a flexible cable (Figure 3). The Stylus incorporates features to allow compatibility with and

RhinAer RELIEF single arm protocol Rev C Final 27JAN2021CONFIDENTIAL

authentication by only the Aerin Console. The connector for the RhinAer Stylus has a pin configuration that prevents its use with other RF generators, making it only compatible with the Aerin Console. Authentication of the Stylus is achieved via a crypto chip that is built into the Stylus handle assembly. The chip is read and written to by the Aerin Console. Information stored on the chip includes the Stylus model information, default treatment parameters (Power 4W, Temperature 60 °C, Duration 12s, Cooling Time 0s), custom treatment setting ranges (Power 3-5W, Temperature 50-70°C, Duration 10-18s, Cooling 9-12s), usage timestamp data, and a count of the remaining treatment cycles (based upon pre-set maximum).

The RhinAer Stylus is temporarily inserted into the nose to access the treated area. The Stylus requires the application of conductive media to the treatment tip prior to use. The conductive media helps to ensure good contact with tissue at all points of the treatment tip to facilitate energy transmission. Application of the RF energy is controlled by a foot switch connected to the Console. The RhinAer Stylus treats symptoms of chronic rhinitis by modifying the tissues of the nasal airway through the use of low doses of radiofrequency energy to destroy tissue in the PNN regions. The low-power radiofrequency energy generates heat within the submucosal tissue, destroying local tissue, mucous cells, and glands, and creating a coagulation lesion. This destruction of tissue in PNN regions improves symptoms of chronic rhinitis.

The procedure requires local anesthesia only. The Stylus is manufactured and supplied sterile and for single use only by Aerin Medical and may be used to treat both nostrils of the patient.

Figure 1. RhinAer Stylus

Figure 2. RhinAer Stylus tip

Figure 3. Aerin Console with RhinAer Stylus

4.9 Risk/Benefit Analysis

4.9.1 Risks

Potential risks associated with the use of the RhinAer Stylus do not differ from commonly used devices and treatments for chronic rhinitis, but due to the nonsurgical nature of the therapy, small treatment area, low energy delivery, and lack of need for general anesthesia, the overall risk to the participant may be less than presented by other surgical treatments.

Potential risks associated with the use of the RhinAer Stylus and the associated local anesthetics are listed below. Participants will be monitored closely as part of this study to allow for early detection of potential problems and prompt treatment if required.

Adverse events or side effects that may occur as a result of the treatment include:

- External deformity
- Blanching (generalized whiteness)
- Bruising including around the orbital area (black eyes)
- Infection
- Bleeding (other than during the treatment at treatment sites and greater than anticipated by the investigator)
- Mucosal changes
- Scar formation leading to nasal obstruction
- Sensory changes at treatment site
- Dry eye
- Vasovagal response secondary to the procedure

Anticipated observations that are expected in and around the treatment area and are considered minor include:

- Inflammation / generalized redness
- Temporary swelling, edema
- Temporary numbness/tingling
- Temporary soreness/pain
- Mild bleeding at anesthetic injection and/or treatment site (not requiring physician-level intervention, such as cautery)
- Temporary nasal obstruction from tissue edema
- Disruption of mucosal flow/intranasal crusting
- Scab formation.

These observations will be assessed in the nasal assessment and recorded at study visits if they occur. Should any of the following require mitigation by the treating physician or be greater in severity or degree of incidence than

RhinAer RELIEF single arm protocol Rev C Final 27JAN2021CONFIDENTIAL

anticipated, they will be considered an adverse event and will be recorded on the study Adverse Event CRF.

Symptomatic improvements may not be achieved in all participants receiving the RhinAer procedure and may not be durable beyond the 3-month evaluation in all participants with relief at 3 months.

4.9.2 Mitigation of Risks

The study was developed based on previous preclinical and clinical experience and includes a number of steps to minimize any additional risks to participants in the study:

- Careful consideration has been given to the inclusion/exclusion criteria in order to select appropriate candidates for treatment.
- Patients will be fully informed of the study requirements prior to enrollment.
- Only physicians with experience in nasal surgical and minimally invasive procedures, and with specific training using the RhinAer Stylus for performing the RhinAer procedure will be permitted to participate in the study.
- The study will be reviewed and approved by an IRB(s)/EC(s) and conducted according to applicable regulations with ongoing review by the IRB/EC.
- Study procedures, follow-up, and study monitoring are designed to detect and respond to any adverse events in a timely manner.
- Preclinical mechanical and bench evaluations have been conducted to demonstrate that the design characteristics of the study device are appropriate for reliable clinical use of the device.
- The Console has been cleared for use in the US by the FDA based in part on prior clinical studies demonstrating safety and efficacy of its use and CE Marking in the EU. The RhinAer Stylus is also cleared for use by the FDA based in part on prior clinical studies demonstrating safety and efficacy of use, and has CE Marking in the EU.

4.9.3 Benefits

The potential benefit associated with the RhinAer procedure is to offer a minimally invasive treatment method that has been shown in a previous study to help alleviate symptoms of chronic rhinitis and which has been cleared for use by the FDA. The RhinAer procedure treats symptoms of chronic rhinitis by modifying the tissues of the nasal airway through the use of low doses of radiofrequency energy to destroy tissue in the PNN regions. The low-power radiofrequency energy generates heat within the submucosal tissue, destroying local tissue, mucous cells, and glands, and creating a coagulation lesion. This

RhinAer RELIEF single arm protocol Rev C Final 27JAN2021CONFIDENTIAL

destruction of tissue in PNN regions improves symptoms of chronic rhinitis. These benefits may last beyond the length of the study.

The procedure will be provided at no cost to participants.

4.9.4 Potential Risks to Participant Confidentiality

In all clinical studies, confidentiality of protected health information may be breached due to study-related activities beyond those of routine clinical care. This risk will be minimized by not entering personally identifying information into the electronic data capture (EDC) system through the study's electronic case report forms (eCRF). Risks to participant confidentiality are further minimized by allowing only authorized individuals to access the EDC system and the database that stores the electronically entered data. The 21CRF Part 11 compliant and validated system maintains audit trails on all entries, changes or corrections to eCRFs. If a person with authority to complete but not sign eCRFs makes changes to an already signed eCRF, the investigator will be required to re-sign the eCRF, thereby protecting the integrity of the data collection process and the data.

4.9.5 Study Justification in Relation to Risk

The study sponsor believes that any additional risks presented by participating in this study are very low and that adequate testing, safeguards, and risk monitoring have been incorporated into the study to further minimize and mitigate the risks relative to the potential benefits, including relief from symptoms of chronic rhinitis, that may be realized by participation in this study.

5.0 Study Schedule and Procedures

This section provides summaries of the study schedule of events and flow of participants through the study, as well as more detailed information on study procedures and processes.

5.1 Schedule of Events

		Treatment		Follow-up					
		Irea	i i catillent		In office Rem			ote	
	Screening	Procedure	Immediate Postprocedure	3 Months ¹ (13 weeks)	6 Months (26 weeks)	12 Months (52 weeks)	24 Months (104 weeks)	36 Months (156 weeks)	
Window (days)	(-30)	(0)	(0)	(± 14)	(± 30)	(± 30)	(± 30)	(± 30)	
Activity / Assessment									
Eligibility	Х								
Consent	Х								
Demographics / Medical History	Х								
Physician Evaluations									
Nasal assessment (physical, endoscopic)	Х	Х	Х	Х					
Current medication use (study relevant)	Х	Х	Х	Х	Х	Х	Х	Х	
Participant Evaluations									
VAS nasal pain			Х	Х					
Rhinitis symptoms (rTNSS, cough, and postnasal drip)	Х			Х	Х	Х	Х	Х	
MiniRQLQ	Х			Х	Х	Х	Х	Х	
Participant Satisfaction Survey				Х	Х	Х	Х	Х	
Adverse Events	Х	Х	Х	Х	Х	Х	Х	Х	

¹Primary analysis endpoint.

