4.2 Study Population

The target population for this study is adults who have exhibited symptoms of chronic rhinitis, such as congestion, rhinorrhea, sneezing, and itching, that may be caused by nonallergic or allergic triggers for at least 6 months. Patients with symptoms due only to seasonal allergies are to be excluded. This study requires significant symptoms demonstrated by an rTNSS ≥ 6 , which includes moderate to severe symptoms of rhinorrhea and mild to severe symptoms of nasal congestion.

Patients who have anatomic obstructions that may limit access to the target treatment area or have altered posterior nasal anatomy due to prior surgery or injury are excluded from participation.

Patients must meet all inclusion and exclusion criteria listed below for participation in the study.

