4.2.1 Inclusion Criteria

- 1. Age 18 to 85 years (inclusively).
- 2. Willing and able to provide informed consent.
- 3. Willing and able to comply with the participant-specific requirements outlined in the Study Protocol.
- 4. Seeking treatment for chronic rhinitis symptoms of at least 6 months duration and willing to undergo an office-based procedure.
- 5. Moderate to severe symptoms of rhinorrhea (rTNSS rating of 2 or 3 for rhinorrhea).
- 6. Mild to severe symptoms of nasal congestion (rTNSS rating of 1, 2 or 3 for congestion).
- 7. $rTNSS \ge 6$.

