5.3 Enrollment and Baseline Assessment

Screening

The investigator or designated research staff will perform an evaluation of the study candidate for study eligibility, which may include a history and physical examination of the nasal area, review of overall medical history, understanding of general health and discussion of any conservative measures used chronic rhinitis. In addition, patients will complete standard questionnaires to document current symptoms associated with chronic rhinitis (rTNSS, MiniRQLQ).

Patients must be diagnosed with chronic rhinitis prior to entry into the study. The use of diagnostic procedures and screening tests to determine a diagnosis and assess whether patients are appropriate candidates for inclusion in the study is an appropriate pre-entry activity. While the availability of the study may be discussed with a prospective participant without first obtaining consent, informed consent must be obtained prior to initiation of any clinical procedures dictated by the protocol that are performed solely for the purpose of determining eligibility to participate in the study. Once the pretreatment assessments are completed the study procedure should be scheduled within 30 days.

Informed consent

Informed consent must be obtained in accordance with FDA regulation 21 CFR Part 50 and ISO 14155. The clinical investigator or designated staff member is responsible for ensuring that IRB/EC approved informed consent is obtained for each participant prior to participation in the study or before undergoing any procedure specific to the clinical investigation. The patient must be fully counseled with an explanation of the study background, study procedure, followup schedule, and informed of their options, risks and benefits, and have every opportunity to ask questions about participation in the study. Any new information obtained during the course of the study that may affect the health of the participant or their decision to continue in the study will be provided to the participant. This process includes a thorough explanation of the informed consent document that the patient will be asked to sign acknowledging that they understand and desire to participate in the study. The explanation and discussion should be conducted in such a way as to:

- answer the participant's questions,
- avoid coercion or influence of patient to participate in the study,
- ensure the patient understands that their legal rights are not waived at any time,

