- use language at a level the patient can understand, and
- ensure the patient understands that after providing signature on the Informed Consent, the patient may still withdraw at any time before, during or after study treatment.

Evaluation of inclusion and exclusion criteria

The Screening Visit / Study Eligibility CRF will be used to document the participant's eligibility status.

Pretreatment (baseline) data and assessments

The following data will be obtained prior to treatment and recorded on the Baseline Visit Demographics and Treatment History CRF:

- Demographics
 - o Sex
 - Height (inches)
 - Weight (pounds)
 - Date of birth
 - Race / Ethnicity
- Nasal symptoms, history of treatments, nasal visual exam
 - History (duration) of rhinitis

- Rhinitis triggers (allergic or nonallergic)
- Medications used to treat rhinitis
- Previous ENT treatments
- Turbinate enlargement, nasal polyps, and other significant findings

The nasal assessment data (each nostril) including photos or video (physical and endoscopic) will be recorded and entered into the eCRF.

Current use of medication, devices, or other therapies for symptoms of chronic rhinitis, including medication name, frequency, and dose will be detailed on the Medication Log.

Rhinitis symptom severity, including the rTNSS, cough and postnasal drip, will be completed by the participant on the rTNSS CRF.

The MiniRQLQ will be completed by the participant on the MiniRQLQ CRF.

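### One screening rTNSS both selects participants and serves as baseline, so the observed mean change and responder percentage include regression to the mean that the plan cannot separate from the procedure's effect

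*Combined protocol and SAP*

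**What the plan says.** **Collection.** Section 5.1 and the Protocol Summary schedule mark "Rhinitis symptoms (rTNSS, cough, and postnasal drip" at screening and then not until 3 months. Table 1 in Section 8.3.2 agrees: form 04 (rTNSS) is listed at the combined Screening / Baseline visit, while the treatment visit lists only forms 05, 06A and 06B. Section 5.3 places the instrument under screening ("patients will complete standard questionnaires to document current symptoms associated with chronic rhinitis (rTNSS, MiniRQLQ") and again under pretreatment data ("Rhinitis symptom severity, including the rTNSS, cough and postnasal drip, will be completed by the participant on the rTNSS CRF"). It adds "Once the pretreatment assessments are completed the study procedure should be scheduled within 30 days".

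**Recall.** Section 4.4.3: "Participants will be asked to self-evaluate their symptom severity over the preceding 24 hours".

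**Entry.** Section 4.2 says "This study requires significant symptoms demonstrated by an rTNSS" of at least 6. Section 4.2.1 adds "Moderate to severe symptoms of rhinorrhea (rTNSS rating of 2 or 3 for rhinorrhea" and a congestion rating of at least 1.

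**Use as baseline.** The same score is the starting point for the paired difference (Sections 6.2 and 6.10), the no-change imputation (Section 6.6) and the 30% responder rule (Sections 4.51 and 6.11). The study has a single arm (Section 6.1). No run-in, repeat baseline or analysis of regression to the mean is planned.

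**The concern.** A one-day symptom score fluctuates. People admitted because the score was high that day will, on average, score lower when next asked, treated or not. Using the selecting score as the baseline puts that fall inside the measured change, and nothing in the design can subtract it.

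This does not damage the test as a test. Section 6.2 defines its target as the mean of 13-week minus baseline scores, and the paired t-test keeps its level for that quantity. The difficulty is interpretation: Sections 2.4 and 4.5 treat the change as evidence of the procedure's effectiveness and of treatment success. At stake is how much of the reported improvement, and of the responder percentage tested against 60%, belongs to the procedure.

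**Working it through.** **1. The plan's own figure.** Inputs from Section 6.3: one-sided alpha 0.025, power 90%, SD 3, distance 1 point. The noncentral t gives n = 97 with power 90.15%, as stated. Allowing 15% loss, 97/0.85 rounds up to 115; the plan enrols up to 140, of whom 140 × 0.85 = 119 remain.

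**2. Size of the artefact.** Artefact A = (1 − r) × (selected mean − source mean), where r is test-retest reliability. The documents give neither r nor the source mean, so both are assumptions. The selected mean is taken as 8.5, the prior study's baseline (Section 1.0), whose entry rules are not given.

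| Source mean | r = 0.9 | r = 0.7 | r = 0.5 |
|---|---|---|---|
| 7.4 | 0.11 | 0.33 | 0.55 |
| 6.5 | 0.20 | 0.60 | 1.00 |
| 5.6 | 0.29 | 0.87 | 1.45 |

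An item-level simulation (four 0–3 items, all three entry rules, no treatment effect, r about 0.85 to 0.47, source mean 6.0 to 7.7) gave falls of 0.19 to 1.18 points. In the settings closest to the prior baseline (selected mean 8.57, SD 1.63) they were 0.25 to 0.90. With a second, independent pretreatment score as baseline, the spurious change was 0.00 to within about 0.01.

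**3. Pull from the imputation.** With treatment effect E and loss L, and if missing participants would have responded like the rest, the imputed mean decrease is (1 − L)(E + A). It exceeds E only if A > E × L/(1 − L):

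| Loss | E = 1 | E = 5.1 |
|---|---|---|
| 5% | 0.05 | 0.27 |
| 10% | 0.11 | 0.57 |
| 15% | 0.18 | 0.90 |

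This takes the whole loss as missing 3-month scores that are imputed.

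**4. The success decision** (n = 140, SD 3). The observed decrease must reach about 1 + 1.98 × 3/√140 = 1.50. If the treatment-caused change were exactly 1 point, the chance of declaring success would be:

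| Loss imputed as no change | A = 0 | A = 0.25 | A = 0.5 |
|---|---|---|---|
| None | 2.5% | 16% | 50% |
| 15% | 0.4% | 4% | 20% |

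With no treatment effect, an artefact of 0.8 gives success in 0.3% of trials with no loss and 0.04% at 15% loss.

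**5. Responders.** Section 6.6 analyses secondary outcomes on available data only, so the imputation offers no offset. A simulation grid matched to a selected mean of 8.2 to 8.8 and SD of 1.5 to 2.0, with r from 0.63 to 0.91, compared the two baselines. In 44 of 48 settings (artefact 0.16 to 0.74; the other four gave 1.0 to 1.1), 60% responders on a procedure-day baseline read as 62–67% on the screening baseline, and 88% read as 89–91%. For the binomial test against 60% (n = 119, upper tail of 2.5% assumed because Section 6.11 states no level), at least 83 responders are needed. The chance of reaching that is 1.8%, 4.8% and 22% at 60%, 62% and 66%.

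**The case against.** The strongest reply is that the plan is open about being a single-arm before-after study, tests only that change, and sets a demanding null. Section 4.4.3 reports that "by distribution-based methodology the MCID was determined to be 0.59 units" and gives anchor-based values from 0.23, so the 1-point margin leaves 0.41 to 0.77 points of headroom. The prior study's change was 5.1 points, with 88% improving by at least 3 points (about 30%). Against those figures the artefact is small, and the 20% to 50% success rates above need a true effect of exactly 1 point, which nothing in the documents suggests. Entry also requires at least 6 months of symptoms (Section 4.2.1) and excludes purely seasonal rhinitis (Section 4.2.2), which may limit fluctuation and place the artefact toward the lower end. All of this stands, except that the prior study was uncontrolled too and its 5.1 points may contain the same artefact.

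A reader might infer that the reported primary effect must be overstated. The documents do not support that. At the planned 15% loss and a 5.1-point effect, the artefact would have to exceed 0.90, and most of the range lies below that. Nor can one say that the imputation cancels a fixed 0.18 points; that holds only for a 1-point effect at 15% loss.

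A reader might also infer that the study could succeed on regression alone. That needs low reliability together with a low source mean: at r about 0.47 and source mean 6.0 the chance is about 10% (n = 140, SD 3), and elsewhere it is at most a few percent in the settings tried.

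It is also fair that a second baseline is only a partial cure. That is a reason to describe the change as uncontrolled, not a reason to leave the selecting score as baseline.

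**Conclusion.** The concern holds as a matter of attribution. The responder percentage and the available-data mean change at 3 months include regression to the mean in the favourable direction, and the plan cannot estimate how much. The imputed primary mean is overstated only when loss is low or the effect is small. The t-test is sound for the quantity it tests, and the success verdict is unlikely to change if the effect is near 5.1 points.

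The size, roughly 0.2 to 1.2 points, rests on assumed reliability of about 0.9 to 0.5 and an assumed source population. The direction needs only reliability below 1 and selection from the upper part of the distribution. This is a cheap improvement worth making, not a flaw that invalidates the primary test.

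**What to change.** - Use the screening rTNSS for eligibility only.
- Add form 04 at the procedure visit, before anesthesia, in both schedules and in Table 1.
- Make that score the baseline for the primary change, the no-change imputation and the responder rule, without re-applying the entry thresholds. Count a procedure-day score of 0 as a nonresponder.
- Report the screening-to-procedure change, and give the change from screening as supportive.
- Where screening and procedure fall on the same day, keep the screening score, flag these participants and show the primary result without them.
- Describe the change as uncontrolled in reports.

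**Cost.** One short form at a visit already attended, an amendment with IRB/EC approval (Section 9.7), and probably a slightly smaller estimated effect. The SD of the change rises by 0.5% to 5% in the 44 calibrated settings. If it rose from 3.0 to 3.3, power at n = 119 for a decrease 1 point beyond the margin would fall from 95.0% to 90.6%.

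**What remains.** Placebo response and natural history are untouched. If day-to-day noise is correlated 0.3 or 0.5 between screening and procedure day, 21–28% or 35–46% of the artefact persists.
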